5.2.4.2 Screening for laboratory evidence of tumour lysis syndrome

Tumour lysis syndrome (TLS) is characterized by metabolic derangements caused by the massive and abrupt release of cellular components into the blood after rapid lysis of malignant cells. The release of the intracellular metabolites can overwhelm normal homeostatic mechanisms, potentially leading to hyperuricemia, hyperkalemia, hyperphosphatemia, hypocalcemia, and uremia. This can result in impaired renal function, and in some cases, in acute renal failure and even death ([R10-4517](#)). To allow for early treatment in case TLS develops, vigilant monitoring is recommended if clinically indicated. During the first 48 hours after the start of the first infusion/injection of BI 836909 in course 1, and during the first 24

Proprietary confidential information.

© 2018 Boehringer Ingelheim International GmbH or one or more of its affiliated companies. All rights reserved.

This document may not - in full or in part - be passed on, reproduced, published or otherwise used without prior written permission.

hours after the start of the first infusion/injection in course 2, the below listed laboratory parameters need to be determined to screen for evidence of a tumour lysis syndrome monitored frequently, i.e. every 4-8 hours between the time points at which a complete safety laboratory has to be performed. The actual date and time of the blood samples should be recorded in the eCRF.

| | |
|--------------|--|
| Haematology | haemoglobin, haematocrit, red blood cell count (RBC), white blood cell count (WBC),+ differential, platelets (PLT) |
| Biochemistry | uric acid, potassium, calcium, inorganic phosphate, lactate dehydrogenase (LDH), creatinine, urea, ferritin. |
| Coagulation | Activated partial thromboplastin time (aPTT), prothrombin time (PT)/international normalised ratio (INR), fibrinogen, D-dimer. |

5.2.4.3 Virology

5.2.4.3.1 Screening for hepatitis B, hepatitis C and human immunodeficiency virus

Patients with active hepatitis B (HBV), hepatitis C (HCV) or laboratory evidence of a chronic infection have to be excluded from the trial, i.e. antigen or antibody positive. The same applies to patients with a human immunodeficiency virus (HIV) infection.

The following laboratory parameters have to be determined at the screening visit and reported in the eCRF: hepatitis B surface antigen (HbsAg), hepatitis B surface antibody (anti-HBs), hepatitis B core antibody (anti-HBc), hepatitis C antibody (anti-HCV), HCV RNA.

Screening for HIV infection should be performed according to local standards. The result of the HIV assessment has to be reported in the eCRF.

5.2.5 Electrocardiogram

A 12-lead resting electrocardiogram (ECG) will be performed in **all patients** at the screening visit and at the beginning of each cycle (except for cycle 1) and at the EOT visit. The ECG will be assessed for pathological results (to be recorded as either baseline condition, concomitant disease or AE) by the investigator. Additional examinations should be done whenever the investigator deems necessary.

For safety monitoring 12-lead ECGs (I, II, III, aVR, aVL, aVF, V1 - V6) will be recorded using an electrocardiograph.

All ECGs will be recorded for a 10 second duration after the subjects have rested for at least 5 min in a supine position.

Proprietary confidential information.

© 2018 Boehringer Ingelheim International GmbH or one or more of its affiliated companies. All rights reserved.

This document may not - in full or in part - be passed on, reproduced, published or otherwise used without prior written permission.

5.2.6 Assessment of other safety parameters

5.2.6.1 Vital signs

Vital signs (blood pressure, pulse rate and body temperature) will be recorded at every visit during screening, treatment and EOT. Additional time points for blood pressure, heart rate and body temperature at the day of start of administration of BI 836909 are: prior to the start of premedication and infusion, then every 30 (± 10) minutes after start of the infusion of BI 836909 for a total of 4 hours and thereafter 3 times a day during hospitalisation or in case of cytokine release syndrome and at each visit. In case of an infusion-related reaction, the investigator should decide whether to intensify or prolong monitoring of vital signs of the patient. Continuous cardiac monitoring should be performed during the hospitalisation for administration of BI 836909, patient surveillance may be modified by the investigator according to tolerability of the infusion during subsequent applications.

5.2.6.2 Physical examination

A physical examination including height (screening only), weight and ECOG performance score including an orienting neurological examination will be performed at screening and at the time points specified in the [Flow Chart](#). The orienting neurological examination should be performed at screening as well as at EOT and daily during hospitalisation (see [Flow charts](#)).

During the physical examination, the patient should be assessed for possible adverse events.

5.3 OTHER

5.3.2 Other assessment(s)

5.3.2.1 Demographics and history

Demographics (sex, birth date, race), and baseline conditions will be collected during the screening visit. A detailed cancer history will be obtained. The date of first diagnosis of MM (month and year may be sufficient) will be recorded in the eCRF. The stage at diagnosis according to the response criteria of the International Myeloma Working Group (IMWG, 2006) at screening should be recorded (see [Appendix 10.1](#)). Previously administered chemo- and immunotherapy will be documented, including start and end dates (year and month may be sufficient), the treatment regimen/protocol with the number of courses (chemo-, immunotherapy), the best response obtained and the date of progression after each prior therapy (year and month may be sufficient). If the patient has received chemotherapy with autologous stem cell support, procedural details, including the treatment regimen prior to stem cell support should be collected. Documentation of previous radiotherapy should include the total radiation dose and radiation field(s). Any myeloma-related previous surgeries which may affect tumour

Proprietary confidential information.

[figure not shown]
© 2018 Boehringer Ingelheim International GmbH or one or more of its affiliated companies. All rights reserved.

This document may not - in full or in part - be passed on, reproduced, published or otherwise used without prior written permission.

assessment in this trial according to the investigator within the past five years should be documented in the eCRF.

5.3.2.2 Concomitant diagnoses

Concomitant diagnoses present at study entry and/or during screening and relevant to the patient's safety during the trial as judged by the investigator will be recorded in the eCRF.

5.4 APPROPRIATENESS OF MEASUREMENTS

Determination of MTD is based on toxicities graded according to CTCAE 4.03 ([R10-4848](#)). The CTCAE criteria are commonly used in the assessment of adverse events in cancer patients. The criteria to be used for evaluation of response ([Appendix 10.1](#)) are well established and scientifically accepted.

Proprietary confidential information.

© 2018 Boehringer Ingelheim International GmbH or one or more of its affiliated companies. All rights reserved.

This document may not - in full or in part - be passed on, reproduced, published or otherwise used without prior written permission.

5.5 DRUG CONCENTRATION MEASUREMENTS AND PHARMACOKINETICS

Blood samples during and at the end of infusion must be taken from the arm opposite to the infusion arm. For patients having a central venous access, PK samples obtained from either forearm. In order not to confound ECG recording, PK samples should be taken after performing the ECG.

If the infusion duration deviates from the scheduled time, the exact start and end times should be recorded in the eCRF. If the infusion stops in between, the stop time and the time when it is started again need to be documented in the eCRF. If the duration of infusion is prolonged or shortened, all following time points of PK and biomarker sampling should be adapted to the time when the i.v. infusion or s.c. injections has ended. Any changes in the rate of infusion should be documented in the eCRF.

Blood for pharmacokinetic analysis will be collected at specified time points during the corresponding treatment cycles (see corresponding [Flow Charts](#); [Appendix 10.2](#)) to determine the concentration of BI 836909. The blood samples for PK analysis will be processed to serum the same way as the ADA samples. The actual sampling date and time for blood samples should be documented in the eCRF. These actual sampling times will be used for determination of pharmacokinetic parameters. The exact clock time of trial medication administration and blood sampling as well as timing of any changes to the infusion flow rate will be documented in the eCRF.

Generally, PK serum samples for BI 836909 determination will be labelled with the study number, subject number, cycle number, visit number, protocol (planned) time and the sample number (according to [Flow Charts](#); [Appendix 10.2](#)).

Detailed handling instructions for serum samples are provided in the ISF as well as the lab-manual.

5.5.1 Pharmacokinetic endpoint(s)

If data allow, the following pharmacokinetic parameters will be evaluated using non-compartmental analysis methods according to the internal BI Standard Operating Procedure (SOP).

Secondary pharmacokinetic endpoint is:

- Serum concentration at steady state (C_{ss}) for c.i.v.

Proprietary confidential information.

© 2018 Boehringer Ingelheim International GmbH or one or more of its affiliated companies. All rights reserved.

This document may not - in full or in part - be passed on, reproduced, published or otherwise used without prior written permission.

5.5.2 Methods of sample collection and storage

5.5.2.1 Blood sampling for pharmacokinetic analysis

[figure not shown]
2,5 mL blood will be taken from a forearm vein or a central venous access in a vacutainer tube containing SSTII separation gel. The vacutainer should be carefully inverted 5 times after sample collection (an inversion is one complete turn of the wrist, 180 degrees and back). Tubes should stand upright for minimum 30 minutes but for a maximum of 2 hours at ambient temperature. The tube should be centrifuged for 10 min at 3,500-4,500 rpm. The specimen has been sufficiently centrifuged when the solid blood components and the liquid are approximately equally separated. The serum must be transferred with a pipette into a cryovial with colored cap (blue cap for PK) and immediately frozen at -20°C until shipment.

After the analysis has been performed the samples will be stored for 5 years and then destroyed.

5.5.2.2 Analytical determinations of samples

A detailed description of the validated assay will be available prior to the start of sample analysis.

[figure not shown]
The remainder samples may be used for immunogenicity assessment if needed.

Proprietary confidential information.

© 2018 Boehringer Ingelheim International GmbH or one or more of its affiliated companies. All rights reserved.

This document may not - in full or in part - be passed on, reproduced, published or otherwise used without prior written permission.

Proprietary confidential information.

© 2018 Boehringer Ingelheim International GmbH or one or more of its affiliated companies. All rights reserved.

This document may not - in full or in part - be passed on, reproduced, published or otherwise used without prior written permission.

5.6.1.4 Immunophenotyping

[figure not shown]
Diagnostic multiple myeloma flow cytometry including MRD

Analysis of myeloma cells in bone marrow will be conducted using a diagnostic flow cytometry panel including markers for CD45, CD38, CD19, CD138, CD56 and kappa/lambda chains. The analysis will be performed centrally. In order to assess minimal residual disease the flow cytometric panel may include 6-color-analysis such as cytIgλ /cytIgκ/CD19/CD56/CD38/CD45 and cytIgλ/CD19/cytIgκ/CD138/CD38/CD45 ([R14-4637](#)). Modifications according to updated guidance are possible.

Proprietary confidential information.

© 2018 Boehringer Ingelheim International GmbH or one or more of its affiliated companies. All rights reserved.

[figure not shown]
This document may not - in full or in part - be passed on, reproduced, published or otherwise used without prior written permission.

Proprietary confidential information.

© 2018 Boehringer Ingelheim International GmbH or one or more of its affiliated companies. All rights reserved.

[figure not shown]
This document may not - in full or in part - be passed on, reproduced, published or otherwise used without prior written permission.

Proprietary confidential information.

© 2018 Boehringer Ingelheim International GmbH or one or more of its affiliated companies. All rights reserved.

[figure not shown]
This document may not - in full or in part - be passed on, reproduced, published or otherwise used without prior written permission.

Proprietary confidential information.

© 2018 Boehringer Ingelheim International GmbH or one or more of its affiliated companies. All rights reserved.

This document may not - in full or in part - be passed on, reproduced, published or otherwise used without prior written permission.

Proprietary confidential information.

© 2018 Boehringer Ingelheim International GmbH or one or more of its affiliated companies. All rights reserved.

This document may not - in full or in part - be passed on, reproduced, published or otherwise used without prior written permission.

6. INVESTIGATIONAL PLAN

6.1 VISIT SCHEDULE

Patients must comply with all inclusion and exclusion criteria prior to the patient enters the study (see [Section 3.3](#)).

All patients should adhere to the visit schedule as specified in the [Flow chart](#). However, in case a patient misses a visit and the patient reports to the investigator between the missed and the next scheduled visit, the procedures that were planned at the missed visit should be done and the actual date and the reason for the delay should be documented in the eCRF. Subsequent visits should follow the original visit schedule of the ongoing cycle unless a treatment pause > one week occurred. Then the next scheduled cycle should be started.

Some flexibility is allowed in scheduling the visits according to the time window specified in the [Flow chart](#) (± 3 days).

If pathological laboratory values or other issues require an additional unscheduled visit, a new eCRF page will be created for the unscheduled visit. At the unscheduled visit, it is sufficient to record only the clinical relevant labs/examinations performed.

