4.1.4.3 Dose reductions and dose delays

Related SAEs/AEs of \geq grade 2 or non-drug related SAEs/AEs of \geq grade 2 deemed intolerable by the patient or the treating physician and not responding to appropriate medical management will result in a pause until resolution to baseline or grade 1. A pause of a maximum duration of 14 days and a dose reduction to the next lower dose level is allowed if clinically indicated. Only one dose de-escalation step is allowed.

DLT events in any cycle, cases meeting the pre-defined hepatic injury criteria (ref. [5.2.2.1](#)) and infusion related reactions or cytokine release syndromes \geq grade 3 will lead to permanent discontinuation in the dose escalation phases. After recovery to baseline or grade 1 continuation of the cycle at the next lower dose tier is allowed. Only one dose de-escalation step is allowed.

CNS events \geq grade 2 irrespective of relatedness that have not resolved to baseline or grade 1 within one week despite treatment interruption will lead to permanent discontinuation in the dose escalation phase. CNS events that have resolved to baseline or grade 1 within one week can be continued at the next lower dose level. Only one dose de-escalation step is allowed.

In case of dose reductions all future courses will also be at the reduced dose level.

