4.1.4.5 Temporary treatment interruption of BI 863909

If a pause of treatment < 14 days occurs within a cycle then the cycle will be restarted at the same or the next lower dose (if clinically indicated) and continued until the pre-scheduled end of the cycle. This dose will be continued in subsequent cycles.

If a pause of treatment occurs and less than 7 days of treatment would remain after restart of the cycle there is an option to skip the last treatment days and continue with the next course as scheduled. However, treatment should not be given for less than 14 days per cycle.

Patients who permanently discontinue treatment for reasons other than DLT will be replaced. Only patients who will receive at least 14 days of treatment in the first course will be evaluable for the primary analysis unless they develop DLT.

For dose levels 2 and higher the trial safety committee may decide to start the subsequent cycles of the affected patient and potentially new patients at this and higher dose cohorts in a stepwise fashion: treatment will be started at 10-30% of the target dose for the first week (but not earlier than 4 days after the stop of infusion in retreated patients). On day 9 the dose may be escalated to the target dose.

The re-start of the infusion should be performed in the hospital under supervision of the investigator.

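### For a cycle 1 pause of 8 to 13 days without a DLT that begins before 14 treated days, protocol Section 4.1.4.5 resumes the cycle (15 to 20 treated days, evaluable for the MTD), but Section 6.1 as written starts the next one (1 to 13 treated days, not evaluable)

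*Protocol*

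**What the plan says.** Protocol Section 4.1.4.5, on temporary interruption, gives the dosing rule: "If a pause of treatment < 14 days occurs within a cycle then the cycle will be restarted". The dose may be kept or lowered by one level, and infusion is then "continued until the pre-scheduled end of the cycle". There is one exception. If fewer than 7 treatment days would be left after the restart, "there is an option to skip the last treatment days and continue with the next course as scheduled". A floor follows: "However, treatment should not be given for less than 14 days per cycle". The same section sets the evaluability rule, restricting the primary analysis to patients with "at least 14 days of treatment in the first course will be evaluable for the primary analysis unless they develop DLT".

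Protocol Section 6.1, on the visit schedule, has a paragraph for the situation "in case a patient misses a visit and the patient reports to the investigator between the missed and the next scheduled visit". It ends by keeping later visits on the ongoing cycle's schedule "unless a treatment pause > one week occurred. Then the next scheduled cycle should be started".

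The other pause limits in the protocol are set at 14 days. Section 4.1.4.3 allows "A pause of a maximum duration of 14 days". Section 4.1.4.4 discontinues patients permanently once an AE-related pause exceeds two weeks. Section 4.2.1.2.3 and the CRS management table (Table 4.1.4.1.4: 1) discontinue for interruptions above 14 days.

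SAP Section 6.3 bases the primary DLT analysis on the MTD evaluation set, defined as treated patients who were not replaced. For the replacement rules it points to protocol Section 4.1.4.5 and adds the safety committee's decision. It does not name the 14-day criterion.

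**The concern.** Both sections cover pauses of more than 7 and fewer than 14 days, and they give opposite instructions: one returns the patient to the interrupted cycle, the other moves the patient on. Neither refers to the other. In cycle 1 the choice decides whether the patient reaches the 14 treated days that the primary endpoint needs.

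Such a pause is foreseeable without a DLT. Under Section 5.2.1.1 a grade 3 infection that responds to treatment within 48 hours is not a DLT. Under Section 4.2.1.2.3 a patient with an active systemic infection needing intravenous anti-infectives is not dosed until the infection has resolved and the anti-infective course is finished. That section discontinues the patient only beyond 14 days, so a hold of 8 to 13 days lies within what the protocol allows.

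At stake is one evaluable patient in a cohort of 3 to 6, and for that patient the infusion days that would have followed the restart.

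**Working it through.** There is no plan figure to reproduce: protocol Section 7.7 states that the sample size is not based on a power calculation. The check is an enumeration of cases.

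**Inputs.** Infusion of 4 weeks = 28 days per cycle (protocol flow chart, footnote 1). Resume rule for pauses under 14 days, skip option below 7 remaining days, floor of 14 days per cycle, and evaluability at 14 days in course 1 (all Section 4.1.4.5). Move-on rule for pauses over 7 days (Section 6.1).

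**Set-up.** Let k be the treated days before a single pause and d its length, in whole days, with k at least 1 and the restart inside the 28-day infusion, so 28 − k − d ≥ 1.

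- Treated days if the cycle is resumed: k + (28 − k − d) = 28 − d.
- Treated days under Section 6.1 as written: k.
- Days left at restart: 28 − k − d.

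| d | Resumed: 28 − d | All k (27 − d) | k ≥ 14 | k ≤ 13 | k ≤ 13 with 7 or more days left |
|---|---|---|---|---|---|
| 8 | 20 | 19 | 6 | 13 | 13 |
| 9 | 19 | 18 | 5 | 13 | 12 |
| 10 | 18 | 17 | 4 | 13 | 11 |
| 11 | 17 | 16 | 3 | 13 | 10 |
| 12 | 16 | 15 | 2 | 13 | 9 |
| 13 | 15 | 14 | 1 | 13 | 8 |
| Total | 15 to 20 | 99 | 21 | 78 | 63 |

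**Pause begins at 14 or more treated days (21 cases).** At most 28 − 14 − 8 = 6 days are left, so the skip option is open and the 14-day floor is already met. The two sections are compatible and the patient is evaluable either way.

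**Pause begins earlier (78 cases).** Resuming gives 15 to 20 treated days; Section 6.1 gives 1 to 13. The skip option does not reconcile them. In 63 cases 7 or more days are left, so it is not open. In the other 78 − 63 = 15 cases using it would leave k ≤ 13 days, below the floor. The infusion days lost under Section 6.1 run from 28 − 13 − 13 = 2 to 28 − 1 − 8 = 19.

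**Pause of exactly 14 days.** Section 4.1.4.3 allows it and Section 4.1.4.4 does not end treatment, but the restart rule in Section 4.1.4.5 stops just short of it. There are 13 cases (k = 1 to 13). Resuming gives 28 − 14 = 14 treated days, just evaluable; Section 6.1 gives 1 to 13.

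**Example (assumed: 10-day infection hold after 5 treated days).** Resumed: 28 − 10 = 18 treated days. Section 6.1: 5.

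**Proposed wording.** Over d = 8 to 14 there are 99 + 13 = 112 cases. Under Section 6.1 as written, 78 + 13 = 91 end below 14 treated days. If the cycle is resumed except when fewer than 7 days remain and at least 14 have been given, none do: resuming gives 14 to 20 days, and skipping requires k ≥ 14.

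**The case against.** The strongest answer is that Section 6.1 was never meant to govern dosing. It is headed as a visit schedule, the sentence closes a paragraph on missed visits, and its subject is later visits. Dosing after a pause has its own section, which is worded as mandatory where Section 6.1 only recommends. A site reading both could reasonably let Section 4.1.4.5 prevail, and the 14-day floor signals that leaving cycle 1 early is off-plan. That reading is possible, and it limits the point to unclear wording with a possible consequence. It does not remove the point: the sentence is triggered by a treatment pause and directs that a cycle be started, and no precedence is given. A site should not have to infer a dosing rule.

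Three stronger readings are tempting, and the documents do not support them.

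- A reader might infer that dose escalation could go ahead on an inadequate cohort. Section 3.1.1 has the safety committee review every cohort before escalation, and it can add patients.
- A reader might infer that the patient drops out of the SAP's MTD evaluation set automatically. That set is defined by replacement. Section 4.1.4.5 replaces patients who permanently discontinue for reasons other than DLT, and a patient moved to cycle 2 has not discontinued. Removal therefore depends on the replacement decision.
- A reader might infer that Section 6.1 is the only restart rule for a pause of exactly 14 days. Section 4.1.4.3 also contemplates resumption, and the CRS table gives restart guidance and discontinues only beyond 14 days.

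The enumeration also gives no frequency, and the documents offer none. CNS events of grade 2 or higher and CRS of grade 2 or 3 that have not improved to grade 1 or below within about a week lead to discontinuation. The conflict therefore concerns mainly infections and other adverse events.

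**Conclusion.** The inconsistency is real and worth correcting, but its reach is limited. For a single cycle 1 pause of 8 to 13 days, without a DLT and beginning before 14 treated days, the two sections lead to 15 to 20 treated days against 1 to 13. The second result is below the protocol's own floor and not evaluable for the primary MTD analysis under Section 4.1.4.5. If the committee replaces such a patient, the cohort needs one more patient and at least 4 more weeks of observation.

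This rests on reading Section 6.1 literally, on one pause counted in whole days, and on a restart inside the 28-day infusion. How often such pauses occur is unknown. Whether the patient would also count as non-compliant under SAP Section 7.3 is a matter of interpretation and is not claimed here.

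**What to change.** **Protocol Section 6.1.** Replace the instruction to start the next scheduled cycle with wording that defers to Section 4.1.4.5, for example: *After a treatment pause of up to and including 14 days, the current cycle is resumed under Section 4.1.4.5 to its planned end. The following cycle may begin on schedule without completing the current one only if fewer than 7 treatment days would be left and at least 14 have already been given.* The present sentence can stay for longer pauses that are not due to an adverse event, which Section 4.1.4.4 does not cover.

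**Protocol Section 4.1.4.5 (minor alignment).** Change the restart rule from under 14 days to 14 days or fewer, to match Sections 4.1.4.3 and 4.1.4.4.

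**SAP Section 6.3 (separate consistency point, useful however Section 6.1 is read).** State that a patient with fewer than 14 treated days in course 1 and no DLT is excluded from the MTD evaluation set, in line with the evaluability rule in Section 4.1.4.5.

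**Cost.** A short protocol amendment with the usual ethics committee and authority approvals (Section 8.1), and one sentence in the SAP. No added patients, visits or analyses.
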